13.2 Sample Size Consideration

Resulting from laboratory studies conducted on the first several patients on this study, the investigative team plans to test higher doses in steroid-refractory patients with aGVHD (separating of Arms into 2A and 2B). This necessitates expanding the number of participants treated on the arms as described below:

Arm 1 Treated Patients	Arm 2A Treated Patients	Arm 2B Treated Patients
Level 1: N = 2, DLT = 0	Level 1: N = 1, DLT = 0	Level 1: N = 1, DLT = 0
Level 2: N = 2, DLT = 0	Level 2: N = 0, DLT = 0	Level 2: N = 2, DLT = 0
Level 3: N = 6, DLT = 0	Level 3: N = 3, DLT = 0	Level 3: N = 4, DLT = 0
Enroll 10 more patients Next dose level 3: N = 2	Enroll 16 more patients Next dose level 3: N = 2	Enroll 13 more patients Next dose level 4: N = 2

- The next dose was calculated with R package “dfcrm”.
- The next dose for Arm 2B was dose level 5, but restrict the dose jump, so the next dose will be dose level 4.

We now anticipate recruitment of 20 participants in each of the 3 arms to complete phase I.

In phase I, based on resources, the maximum number of allowable evaluable patients is 20 for each arm (total of 60 for all three arms). The simulations show it should be sufficient and safe to define the MTD for future efficacy trials.

For Arm 1 or 2A, if fewer than 13 patients are enrolled at the MTD, the phase II extension trial using Simon's two-stage Minmax design will require 26 patients to test the null hypothesis that the response rate at day 28 is <40% versus the alternative that the response rate is $\geq 65\%$ after assuming 80% power and a significance level of 0.05 and using a maximum of 26 patients. We will choose the rule that minimizes the expected sample size giving a true response rate equivalent to the null hypothesis. We expect that for each arm, phase I and II will require approximately 33 patients due to use of patients from the phase I trial in the phase II extension ([table 2](#) shows about 13 patients will be treated under MTD). But the sample size for each

arm could be as high as 44 when only two patients were treated at MTD in phase I. Therefore we expect the sample size of the phase I/II study for Arm 1 and Arm 2A will be 66 to 88 patients.

For Arm 2B, same as the other two arms, if fewer than 13 patients are enrolled at the MTD, the phase II extension trial using Simon's two-stage Minmax design will require 26 patients to test the null hypothesis that the response rate at day 28 is <40% versus the alternative that the response rate is $\geq 65\%$ after assuming 80% power and a significance level of 0.05 and using a maximum of 26 patients. We expect that for each arm, phase I and II will require approximately 37 patients due to use of patients from the phase I trial in the phase II extension ([table 4](#) shows about 9 patients will be treated under MTD). But the sample size could be as high as 44 when only two patients were treated at MTD in phase I. We expected the sample size of phase I/II study for Arm 2B will be 37 to 44 patients.

The number of evaluable patients per year will be approximately 20 for each arm. We expect accrual to be completed within 7 years.

13.3 Statistical Analysis

SAS 9.3 (Cary, NC, USA) will be used for the statistical analyses. For binary endpoints such as toxicity, summary statistics including proportions and their 95% confidence intervals will be calculated for each arm. All toxicity and safety assessments will be presented in the data listings and summarized with descriptive statistics. Response at day 28 will be estimate with simple proportions and descriptive plots.

The secondary endpoint, proportions of response among the surviving patients at day 7, 14, 56 and 180, treatment failure proportion for acute GVHD at day 28, 56 and 180 after initiation of protocol therapy, the incidence of acute GVHD flare after CR/PR requiring increase of steroids or other systemic treatment at days 28, 56, and 180 will be estimated. Overall survival and disease free survival probabilities after the initial treatment will be estimated using Kaplan-Meier's method. Treatment-related mortality and the incidence of chronic GVHD after the initial treatment will be estimated by competing risk analysis. For other correlative endpoints, continuous measures will be summarized with mean and SD for each arm and time point (if skewed, we will report median and interquatile range) and categorical measures will be summarized with frequency and percentage.

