1.3 Correlative Objectives

- Pharmacokinetics (clearance, half-life, volume of distribution) of the both the hCG and EGF components of urinary hCG when administered to patients with GVHD
- Monitoring for hormonal effects via determination of serum concentrations of hCG, estradiol, progesterone, and testosterone on days 7, 14, 28, and 56, compared to baseline
- Collection of blood samples for measurement of immune and tissue damage/repair biomarkers to determine change from pre-treatment levels to levels obtained on days 7, 14, 28, and 56 post-treatment
- Analysis of previously collected skin and/or gastrointestinal biopsies for biomarkers of refractory aGVHD and response to therapy

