Subcutaneously-delivered urinary hCG has safely been given to both men and women for endocrinologic indications, with data regarding safety and efficacy spanning over 4 decades [23, 24, 25, 26, 27]. Severe reactions including arterial thromboembolism and ovarian hyperstimulation syndrome occur in <1% of patients. The doses administered on this protocol are within the range of established standard of care dosing for endocrinologic indications today. Similar low doses of urinary hCG given to a cohort of patients with steroid-refractory chronic GVHD was well tolerated. Therefore, we believe the safety risks of this study are very minimal. However, the

doses required to significantly increase plasma and tissue EGF levels and exert immunologic effects are not known, making the studies proposed herein necessary for further repurposing of the drug.

3 Summary and Rationale

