HCG is a hormone critical for the development of maternal immune tolerance towards a fetus during pregnancy, arguably the most commonly encountered and effective example of induced immune tolerance in nature. HCG induces immune tolerance in pregnancy by mechanisms including induction of indoleamine 2,3 dioxygenase (IDO) and expansion of endogenous regulatory T cells (Tregs), both of which are protective against GVHD. Therefore, hCG may be effective in promoting immune tolerance in aGVHD. Importantly, a urinary-derived preparation of hCG has already shown early promise in inducing tolerance and reversing organ damage without untoward toxicity in 12 of 20 (60%) of patients with heavily pre-treated patients with steroid-refractory or intolerant chronic GVHD [22].

The objective of this study is to test for the first time the use of supplemental EGF and hCG (Pregnyl®) as an adjunct to facilitate improved mucosal healing and immune tolerance in addition to accepted, standard immunosuppressive therapy in the setting of high-risk (Arm 1) and steroid-refractory (Arm 2) aGVHD. Our central hypothesis is that administration of urinary hCG and EGF will provide (a) EGF for facilitation of gastrointestinal healing and (b) hCG for induction of immune tolerance, while not worsening the rates of infectious or other complications, in patients with severe aGVHD. However, the optimal supplemental doses of EGF necessary to achieve an epithelial restitution effect are not known. Therefore, this study will use the Continuous Reassessment Method (CRM) to test up to five dose levels of Pregnyl® in order to identify the maximum tolerated dose (MTD) by each patient cohort (high-risk (arm 1), steroid dependent (arm 2A) and steroid-refractory (arm 2B)). We will determine pharmacokinetics of both the EGF and hCG components of urinary HCG and identify correlative biomarkers of aGVHD response. The pharmacokinetic and correlative studies would not be possible without intercollegiate collaborations. The knowledge gained from these aims will provide critical feasibility, preliminary safety, and correlative data for efficacious dose selection and identification of leading biomarkers for the phase II expansion of this trial. These data will be necessary to successfully compete for National Institutes of Health or similar funding for a larger scale, multicenter trial, if the approach proves to be feasible, tolerable, and efficacious in this initial study.

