Urinary HCG is an inexpensive, commercially-available hormone with a long track record of safety and tolerability. Therefore, if effective, we anticipate this could quickly be repurposed into a standard adjunctive treatment for high-risk or refractory aGVHD.

The first goal of this study is to find the dose of Pregnyl® needed to at least double patients' plasma EGF levels from baseline levels while not exceeding the maximum tolerated dose. Our preliminary data indicate that baseline plasma EGF levels are in the range of 10-30 pg/ml, whereas the median plasma EGF level of a normal allogeneic HCT recipient without aGVHD is over 10-fold higher at 140 pg/mL.

Dose justification: The doses selected for testing in this trial are within the range of doses of Pregnyl® used for endocrinology purposes today and do not represent "high" doses. The standard dose for ovulation trigger is 10,000 USP of the hCG component, which is more than double the amount that patients on the highest dose level on this protocol will receive. The starting doses for this protocol are estimated to be the minimum sufficient to determine an increase in plasma EGF with therapy. The 1-week cumulative EGF dose obtained from Pregnyl® at dose level 1 is expected to be equivalent to approximately 50% of the circulating EGF in a typical patient with severe aGVHD. The 1-week cumulative EGF dose at dose level 2 is expected to be

approximately 100% of (effectively doubling) circulating EGF in patients with severe aGVHD. Each lot of Pregnyl® will be tested for EGF content prior to administration so that the precise EGF dose administered is known.

4 Study Design

This multi-center phase I/II study will use Continual Reassessment Method (CRM) to establish a maximum tolerated dose (MTD) of human chorionic gonadotropin and epidermal growth factor supplementation (hCG) as an adjunct to facilitate improved mucosal healing and immune tolerance in conjunction with accepted, standard immunosuppressive therapy in the setting of high-risk (Arm 1), steroid dependent (Arm 2A), and steroid-refractory (Arm 2B) acute graft-versus-host disease (aGVHD).

Enrollment and dose escalation of Pregnyl® will be independent for each arm.

Arm 1, Phase I: For each arm up to 5 dose levels of Pregnyl® will be tested; however dose levels -1 and -2 will be used only if dose level 1 proves too toxic. In addition to Pregnyl®, patients will continue on their current standard of care aGVHD treatment.

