7.3 Arm 2B – Steroid-Refractory aGVHD

Standard of care immunosuppression, plus Pregnyl® (hCG supplementation) at assigned dose subcutaneously every other day for 7 doses.

If a patient has a toxicity that fits the definition of dose limiting as defined in the phase I section below, the patient will discontinue study treatment.

Continue protocol treatment through day 14. Assess response at day 14:

- **If a complete or partial response**, the patient is eligible to receive Pregnyl maintenance at the same dose twice weekly for 10 doses beginning day 15 to 17. Refer to [section 9](#) for response definitions.
- **If no response**, the patient will be taken off study treatment

Pregnyl® dose level assignment will be done by treatment arm, with Arm 2 independent of Arm 1.

For phase I, up to 7 dose levels of Pregnyl® will be tested; however dose levels -1 and -2 will be used only if dose level 1 proves too toxic. The reason for this expansion is lack of rise in plasma EGF levels with Pregnyl therapy in patients with the most severe aGVHD in the first 6 patients in phase 1.

Dose Level	Dose
-2	125 USP hCG/875 pg EGF/m ²
-1	250 USP hCG/1,750 pg EGF/m ²
1 (start)	500 USP hCG/3,500 pg EGF/m ²
2	1,000 USP hCG/7,000 pg EGF/m ²
3	2,000 USP hCG/14,000 pg EGF/m ²
4	3,500 USP hCG/24,500 pg EGF/m ²
5*	5,000 USP hCG/35,000 pg EGF/m ²

***NOTE: To avoid using vials from more than one Lot of study product, the maximum dose is either (1) the contents of a single 10,000 IU vial, or (2) a maximum dose of 10,000 IU from multiple vials. All vials used should be from the same Lot.**

The 1st 2 patients will be enrolled in dose level 1. The next cohort of 2 patients will not begin treatment until all patients in the current cohort has reached day 21 to assess for dose limiting toxicity (DLT).

DLT is defined as any of the following occurring by day 21 after the 1st dose of Pregnyl® (phase I component only):

- In males and females: Grade 2-4 thromboembolic event (CTCAE v4) i.e., any thrombosis more severe than a superficial venous thrombosis develops and treatment with anticoagulation is required
- In males and females: Grade 3-4 ascites (CTCAE v4)
- Specific to females: Grade 3-4 ovarian hyperstimulation syndrome, defined as the rapid development of enlarged, cystic, painful ovaries—refer to [section 11.2](#) for CTCAE grading guidance

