10.1 Correlative Studies and Hypotheses

1. Pharmacokinetics: Clearance, half-life, and volume of distribution of the both the hCG and EGF components of urinary hCG when administered to patients with GVHD. This objective tests the hypothesis that as enteropathy improves, the PK profile of both hCG and EGF will change.
2. Hormonal effects: concentrations of hCG, estradiol and progesterone, and testosterone at baseline, and on days 7, 14, 28, and 56 of protocol treatment. This objective tests the hypothesis that any increase in sex hormones induced by the hCG will be reversible and associated with no adverse events.
3. Biomarkers of response in routine clinical laboratory parameters: This objective tests the hypothesis that those receiving HCG will have (a) higher circulating numbers of total lymphocytes, monocyte, platelets, and albumin levels as measured by routine clinical laboratory testing and that all will correlate positively, with HCG treatment and plasma levels of both EGF and hCG.

The following studies detailed below in number 4-7 will be exploratory laboratory studies performed on blood samples collected for the study protocol. At each time point, the following samples will be collected:

For patients ≥ 40 kg

- 60 ml of heparinized blood (green top tubes) for PBMCs, and plasma stored in 15 x 1 ml aliquots.

For patients < 40 kg

- *Collect up to 2 cc/kg to a maximum of 65 ml total blood volume for placed in green top tubes. Plasma will be stored in 1 ml aliquots.*

4. Angiogenic biomarkers of response: This objective tests the hypothesis that higher plasma levels of EGF and VEGF-A and lower levels of follistatin will be observed in those receiving HCG treatment and will correlate with response to treatment.
5. Suppressive/regulatory markers of response: This objective tests the hypothesis that higher blood levels of suppressive/regulatory cytokines cells (IL-10, IL-22 – measured by multiplex array, and regulatory T cells – measured by flow cytometry) will be observed in those receiving HCG treatment and correlate with response to therapy.

6. Inflammatory markers of response: This objective tests the hypothesis that lower blood levels of inflammatory markers (TNF α , IL-6, IL-17, IL-33, – measured by multiplex array) will be observed in those receiving HCG treatment and correlate with response to therapy.

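### Section 13.3 summarises plasma EGF by arm and time point only, so it cannot address the Section 3 goal of finding the dose that doubles EGF (minor; mainly Arm 2B)

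*Combined protocol and SAP*

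**What the plan says.** Section 3 states that the first goal is to find the dose that at least doubles patients' "plasma EGF levels from baseline levels while not exceeding the maximum tolerated dose". It makes predictions by dose level: the one-week cumulative EGF dose should be about 50% of circulating EGF at level 1 and, at level 2, "approximately 100% of (effectively doubling) circulating EGF in patients with severe aGVHD". It also says the study will supply "correlative data for efficacious dose selection and identification of leading biomarkers for the phase II expansion of this trial". Section 2 gives the motivation: the "doses required to significantly increase plasma and tissue EGF levels and exert immunologic effects are not known, making the studies proposed herein necessary".

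Section 1.3 lists biomarker sampling "to determine change from pre-treatment levels to levels obtained on days 7, 14, 28, and 56 post-treatment" as a correlative objective. Section 10.1 plans pharmacokinetics ("Clearance, half-life, and volume of distribution of the both the hCG and EGF components of urinary hCG") and hypothesises that higher plasma EGF will be seen in treated patients and will correlate with response.

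The analysis text for these measures is one sentence in Section 13.3. It reads that "continuous measures will be summarized with mean and SD for each arm and time point (if skewed, we will report median and interquatile range"; categorical measures get frequency and percentage.

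Section 7.3 explains the two extra dose levels in Arm 2B: "The reason for this expansion is lack of rise in plasma EGF levels with Pregnyl therapy in patients with the most severe aGVHD", among the first 6 phase I patients.

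**The concern.** The goal is a statement about dose: which level brings a patient's EGF to at least twice that patient's own baseline. The planned summary has neither the dose nor the patient's own baseline in it. Each arm treats patients at several levels, so a mean or median for the arm at day 7 or day 14 mixes them.

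What is at stake is dose information for a later trial. In Arm 2B the team has already extended the dose range because of EGF. The summary as written would not show whether the higher levels were followed by higher EGF, or whether a lower level did as well. Toxicity may not separate the doses either: Section 13.2 reports no DLT in the 21 patients treated so far (10 in Arm 1, 4 in Arm 2A, 7 in Arm 2B), all at levels 1 to 3.

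**Working it through.** The plan states no figure to reproduce here. The check is what the Section 13.3 summary pools and what it can tell apart.

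**1. The goal in numbers.** Section 3 puts baseline EGF at 10-30 pg/mL, so doubling means at least 2 × 10 = 20 to 2 × 30 = 60 pg/mL, depending on the patient. Because the target depends on each patient's baseline, it needs a within-patient ratio.

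**2. Dose range pooled within an arm** (Sections 7.1 to 7.3, level 1 to top level):
- Arms 1 and 2A: 2,000 / 500 = 4-fold.
- Arm 2B: 5,000 / 500 = 10-fold.

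**3. Share of phase I patients below the top level** (Section 13.2 counts, assuming that remaining patients go to the top level as soon as allowed):

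| Arm | Below top level | Share of 20 |
|---|---|---|
| 1 | 2 + 2 = 4 | 20% |
| 2A | 1 + 0 = 1 | 5% |
| 2B | 1 + 2 + 4 = 7 at levels 1-3, plus 2 at level 4 = 9 | 45% |

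For Arm 2B, the expected numbers in Table 4 give 0.2 + 0.0 + 2.3 + 2.9 + 3.1 + 2.9 = 11.4 of 20, or 57%. If phase II completes with 26 patients at level 5, the share falls to 9 / (9 + 26) = 26%, or 11.4 / (11.4 + 26) = 30% from Table 4. Pooling is therefore mainly an Arm 2B problem.

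**4. What the pooled summary cannot separate (illustration only).** In Arm 2B take 9 patients below level 5 and 11 at level 5, and suppose that 11 of the 20 double their EGF. The number of doublers at level 5 can lie anywhere from max(0, 11 − 9) = 2 to min(11, 11) = 11. Two cases inside that range:
- Steep: 0 of 9 below level 5 and 11 of 11 at level 5.
- Flat: 5 of 9 (56%) below level 5 and 6 of 11 (55%) at level 5; 5 + 6 = 11.

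The same 20 values give the same mean, SD, median and interquartile range in both cases, because none of these statistics uses the dose label. This is true of any pooled summary. It shows what the statistic cannot do; it does not measure a likely loss.

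**5. Whether another section fills the gap.** Section 1.3 names change from pre-treatment but gives no method. The Section 10.1 hypotheses relate EGF to treatment and response, not to dose level. Clearance, half-life and volume use the administered dose but do not report whether plasma EGF reached twice baseline. Dose assignment in Section 13.1 uses DLTs alone. No section gives an EGF analysis by dose.

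**6. Precision a by-dose table would have.** Levels used so far hold 1 to 6 patients each. Exact 95% intervals: 0/1 gives 0 to 97.5%; 0/4 gives 0 to 60%; 0/6 gives 0 to 46%; 8/11 gives 39 to 94%.

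**The case against.** The strongest reply is that no formal objective is left unanalysed. Doubling appears only in the Section 3 rationale; the phase I objective in Section 1.1 is the MTD; and Section 10.1 places the plasma EGF work among exploratory laboratory studies, for which a short descriptive plan is ordinary. This stands, and it limits the weight of the point. It does not remove the mismatch: the protocol calls doubling its first goal, and the one method it states cannot address it.

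A reader might infer that the trial could end unable to answer the question. The documents do not support that. Dose level, lot EGF content and the baseline, day 7 and day 14 samples are all recorded, and Section 13.3 does not forbid further tables. The team has already examined EGF in early patients without a Section 13.3 instruction. Baseline is also a sampling time, so group values before and after treatment would appear side by side. What is missing is a stated time point, threshold and breakdown by dose, fixed before the data are examined.

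A reader might also infer that a by-dose table would show whether the drug raised EGF. It would not. Section 2 reports that, in an earlier multicentre treatment trial, plasma EGF rose by day 28 in complete responders to initial therapy and fell in non-responders. In an uncontrolled study, a rise therefore mixes drug effect with recovery. In addition, Section 10 allows visits ±2 days under every-other-day dosing, so time since last dose varies within an arm as well as between arms.

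**Conclusion.** The point holds as a minor one. The Section 13.3 summary by arm and time point pools dose levels and omits within-patient change, so it cannot address the goal in Section 3 or fully serve the change objective in Section 1.3. It matters mainly in Arm 2B, where 45 to 57% of phase I patients would be below the top level; this assumes the Section 13.2 allocation with escalation as soon as allowed, or the Table 4 expectations. In Arms 1 and 2A the shares are 20% and 5%.

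It would go too far to say that the primary objective or the phase II dose is compromised. Sections 7.1 to 7.3 set the phase II dose at the MTD whatever EGF does, and no participant's treatment depends on this summary.

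**What to change.** Add one descriptive table and one plot for plasma EGF to Section 13.3, and leave the MTD rule unchanged.

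- **Measure:** ratio to the patient's own baseline at day 7 (Arm 1, pre-dose sample) and day 14 (Arms 2A and 2B). These are the response assessments, after which non-responders stop the drug.
- **Table:** by arm and dose level, give n, median and range, and the proportion with a ratio of 2 or more with exact 95% interval.
- **Plot:** the ratio against the EGF dose actually given, from lot-tested content and the 10,000 IU cap at level 5. The cap binds above 10,000 / 5,000 = 2.0 m²; at 2.5 m² the dose is 10,000 / 2.5 = 4,000 USP/m², 80% of nominal.
- **Response and timing:** record time since last dose, and show results by response status or mark responders on the plot. Do not compare arms, because sampling falls at different points in the dosing interval.
- **Status:** state that the table is exploratory, cannot by itself attribute a rise to the drug, and does not select the phase II dose. A sentence in Section 3 should say the same.

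The cost is one paragraph in Section 13.3 and one sentence in Section 3. The samples and lot testing are already planned, so no new visits, samples or patients are needed; time since last dose is the one item to make sure is recorded. The main downside is small cells, so the table will describe and not decide.
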